### b) Primary Performance Endpoint

The Primary Performance Endpoint is defined as the ability to perform binary classification of individual electrophysiological parameter measurements by distinguishing local regions with substantial red blood cell content (RBC-positive) from regions with negligible red blood cell content (RBC-negative) in the occlusion. This endpoint can be understood as the ability for an automated system to rank individual electrophysiological measurements in the occlusion according to the local scale content of RBC (the predicted RBC-content score).

The ability to perform binary classification will be evaluated by the sensitivity (true positive rate) and the specificity (false positive rate) for varying detection threshold. Based on those 2 metrics, the Area under the Receiver Operator Characteristic curve (AUC of ROC) and its 95% confidence intervals (CI)

will be calculated. An AUC of 0.85 is assumed computed from the RBC-content score predicted on the validation dataset only with a maximal width of 0.1 for the 95% confidence interval.

The 'gold standard' is defined as the binary classification of the local regions into RBC-positive or RBC-negative content performed by the Sensome experts. This labelling, considered as ground truth, is made by (at least) two independent SENSOME experts that cumulate the relevant experience in electrochemical impedance measurements of different biological tissues from previous non-clinical research. The comparator will be the binary classification determined by the CSGS model developed by phenomenological modelling. The model will be developed on the data of the development dataset while it will be validated on the data of the validation dataset.

The single electrode pair measurement is defined as the response to an applied micro-current through an electrode pair. Such a response is referred to as 'the electrophysiological parameter': it depends on the arrangement and type of cells and interspersed biochemical components. The response across a single electrode pair is composed of a set of real numbers (up to 32 for CSGS) which are not independent; this set of numbers is referred to as a 'spectrum' since it forms the response as the micro-current frequency is swept across a pre-defined range. This is also referred to as a 'local-scale measurement'. A measurement triggered by the Cloviz software collects at a given time point the spectrums from a pre-defined set of electrode pairs. This is also referred to as a 'sensor-scale measurement' since it sweeps the electrode pairs of the sensor.

The CSGS will be inserted and up to 6 measurements will be done: 1 measurement distal to the access catheter in circulating blood (this is the reference measurement), 1 measurement proximal to the site of occlusion, 2 to 3 measurements inside the occlusion and 1 measurement at the most distal advancement of the guidewire (ideally distal to the occlusion). The collection of measurements made in contact with the clot is referred to as the 'clot-scale' measurement.

[figure not shown]

Figure 1: Schematic view of the sensor presenting the different scales of measurements.

Data from the CSGS is synced to the cloud database. These data are processed offline. Individual electrophysiological measurements are annotated manually by Sensome experts by inspecting the signal and the histological content from the full clot.

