**Clinical investigation plan - CLOT OUT**

content (RBC-negative) in the occlusion. This endpoint can be understood as the ability for an automated system to rank individual electrophysiological measurements in the occlusion according to the local scale content of RBC (the predicted RBC-content score). Evaluation is based on expert labelling of individual electrophysiological measurements as a binary outcome: RBC-positive (region with substantial RBC content) and RBC-negative (region with negligible RBC content). This labelling, considered as ground truth, is made by (at least) two independent SENSOME experts that cumulate the relevant experience in electrochemical impedance measurements of different biological tissues from previous non-clinical research.

- The performance of the CSGS model will be assessed by the performance metric Area Under the Receiver Operator Characteristic curve (AUC of ROC) computed from the RBC-content score predicted on the validation dataset only.
- The ROC curve will be defined by the sensitivity (true positive rate) on the Y-axis and 1-specificity (false positive rate) on the X-axis. The ground truth is defined as the binary classification of the local regions into RBC-positive or RBC-negative content performed by SENSOME experts.
- The comparator will be the binary classification score determined by the CSGS model. The CSGS model will be developed using interventions from the development phase (Development Performance Population) while it will be validated on the impedance data from the validation phase (Local-Scale Performance Population).

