**15.7 BIAS**

To minimize bias, an independent Data Safety Monitoring Board (DSMB) (see section 20.3) will be responsible for monitoring safety and performance aspects of the study. The DSMB consists out of an uneven number of experts in the field, enabling the assessment and conclusion with majority votes. If needed, the DSMB may invite ad hoc team members, such as statistical support. These ad-hoc members will refrain of voting. To review safety events happening in the study – for some events, the DSMB may be requesting additional information from the investigational site or the core lab to allow a comprehensive review. DSMB will be responsible of adjudicating the primary safety endpoint.

Secondly, to evaluate the Primary Performance Endpoint a binary classification of individual electrophysiological parameter measurements into 'RBC-positive' and 'RBC-negative' is performed by 2 SENSOME experts independently. In case of discrepancies, a 3rd expert will decide on the classification. This process cannot be performed by independent reviewers. Following SENSOME's internal procedure (SEN\_QAS\_SOP\_1010), experts involved in annotating data shall not inspect the incoming validation dataset before the development is declared finished (the prediction models being fixed). As dataset inspection is also routine to detect anomalies, another SENSOME expert not involved in the development could be designated in the transition period (when the development phase is not terminated but the development set is completed).

Thirdly, an expert in the field of histopathology from an independent Core Lab (Mayo Clinic) will perform the histopathological analysis of the clots. The core lab will be blinded for the results of the CSGS. Rules of operation and responsibilities are outlined in the Core Lab Instructions.

Fourthly, another independent core lab (UCLA) will check the images. The imaging Core Lab will be set-up by 2 experienced readers. Both will check independently the pre-procedural, procedural and post-procedural images. Both readers will assess the primary safety endpoint. In case of disagreement between the 2 readers, a decision will be made by consensus. Rules of operation and responsibilities are outlined in the Core Lab Instructions.

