## 7. Bias

Since this is a single-arm study, no randomization is performed. Investigator, nor patients are blinded for the treatment.

To minimize bias, an independent Data Safety Monitoring Board (DSMB), also known as a Data Monitoring Committee (DMC), will be responsible for monitoring safety and performance aspects of the study. Rules of operation and responsibilities will be outlined in the DSMB Charter.

The DSMB consist out of an uneven number of experts in the field, enabling the assessment and conclusion with majority votes. If needed, the DSMB may invite ad hoc team members, such as statistical support. These ad-hoc members will refrain of voting. To review safety events happening in the study – for some events, the DSMB may be requesting additional information from the investigational site or the Core Lab to allow a comprehensive review. DSMB will be responsible of adjudicating the primary safety endpoint.

Secondly, to evaluate the Primary Performance Endpoint a binary classification of individual electrophysiological parameter measurements into 'RBC-positive' and 'RBC-negative' is performed by 2 Sensome experts independently. In case of discrepancies, a third expert will decide on the classification. This process cannot be performed by independent reviewers. Experts involved in annotating the development set shall not inspect the incoming validation dataset before the development is declared finished (the prediction models being fixed). As dataset inspection is also routine to detect anomalies, another Sensome expert not involved in the development could be designated in the transition period (when the development phase is not terminated but the development set is completed).

Thirdly, an expert in the field of histopathology from an independent Core Lab (Mayo Clinic) will perform the histopathological analysis of the clots. The Core Lab will be blinded for the results of the CSGS. Rules of operation and responsibilities are outlined in the Core Lab Instructions.

Fourthly, another independent imaging Core Lab (UCLA) will check the images. The imaging Core Lab will be set-up by 2 experienced readers. Both will check independently the pre-procedural, procedural and post-procedural images. Both readers will assess the primary safety endpoint. In case of disagreement between the 2 readers, a decision will be made by consensus. Rules of operation and responsibilities are outlined in the Core Lab Instructions.

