#### Local-Scale Performance Population

This population includes patients for whom data was collected by the CSGS during at least 1 tag in the clot based on expert labelling excluding patients from the Development Performance Population. Data of this population will be used during the validation phase to validate the model built during the development phase.

The analysis of the primary performance endpoint will be performed on data from the Local-Scale Performance Population. Performance assessment during the validation phase will be done only on tags in the clot.

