## c) Statistical analysis methods

### i. Statistical Procedures

A major objective of this study is to evaluate the prediction model(s) of the Clotild® Smart Guidewire System. These prediction models are based on physical properties of the impedance measurements captured by the sensor, complemented with a comparison to suitable labels for each endpoint (a.k.a. phenomenological modelling). The impedance dataset that will be constructed during the clinical investigation should serve to develop the prediction models (model development) and to evaluate their prediction accuracy (model evaluation). Such an evaluation methodology is inspired from Good Machine Learning Practice for Medical Device and avoids any optimistic bias.

Given the necessity to isolate a validation set free of any model optimization to obtain unbiased generalization scores, the dataset will be split into two pieces:

1. **The development dataset**, where model optimizations is being made to arrive at a single particular model trained on the full development dataset.
2. **The validation dataset** that is solely used to assess the performance of the model.

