### **Validation dataset**

After completion of the development phase, data of the following interventions will be used in the validation dataset. The validation dataset shall be used to assess the generalization performance of the model(s) developed during the development phase. When moving to the validation stage, all steps used from input data, i.e. individual impedance spectrums for each electrode pair, to the score prediction shall be fully determined. When moving to the validation phase the model(s) shall be locked, remaining unchanged during the course of the validation phase.

This same procedure of splitting the dataset into two sets (development dataset and validation dataset) will be performed for the primary performance endpoint assessment as well as for the secondary and tertiary endpoint assessments.

Confidence intervals will be computed with the bootstrap.

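### The labels behind the primary AUC are partly read from the impedance signal that the model scores, so the AUC shows agreement with expert labels and does not by itself establish local RBC accuracy

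*SAP*

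**What the plan says.** - **Reference standard.** Protocol 15.4.1: "This labelling, considered as ground truth, is made by (at least) two independent SENSOME experts". SAP 4.b says the same, calls it the gold standard, and gives the method: "Individual electrophysiological measurements are annotated manually by Sensome experts by inspecting the signal and the histological content from the full clot". Protocol 15.4.1 cites the experts' impedance experience and does not mention histology. Neither document gives a cut-off between substantial and negligible RBC content, or says how signal and histology are weighed.
- **Index test.** SAP 8.c.i (Validation dataset) requires at lock that "all steps used from input data, i.e. individual impedance spectrums for each electrode pair, to the score prediction shall be fully determined". The score is thus a function of the spectra.
- **Histology.** SAP 8.a has three slices per clot, averaged. SAP 7 has the core lab blinded to CSGS results.
- **Safeguards.** Protocol 15.7 and SAP 7 provide two independent reads, with a third expert for disagreements. The model is locked before validation. On outside readers the SAP says: "This process cannot be performed by independent reviewers". On access before lock, Protocol 15.7 says that "experts involved in annotating data shall not inspect the incoming validation dataset before the development is declared finished". SAP 7 names a narrower group: "Experts involved in annotating the development set shall not inspect the incoming validation dataset before the development is declared finished".
- **Test set.** Protocol 15.2 admits patients by tagged clot contact. SAP 8.b admits them by expert labelling of the tag and adds: "Performance assessment during the validation phase will be done only on tags in the clot".
- **Bias statement.** SAP 8.c.i, matching Protocol 15.3: "Such an evaluation methodology is inspired from Good Machine Learning Practice for Medical Device and avoids any optimistic bias".

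**The concern.** When the reference label is partly read from the index-test signal, the two can agree for reasons unrelated to the quantity of interest (incorporation bias). Here the model is phenomenological, and Protocol 15.5 says that its design was guided by the sponsor's experience with the signal. The labellers are sponsor experts chosen for experience with impedance measurement. Some sharing of rules between model and label is therefore plausible.

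Splitting the data and locking the model prevents tuning to the validation set. It does nothing about a label that contains the signal. The written access restriction also ends at lock: neither document requires labelling to come before scoring or keeps scores from the annotators afterwards.

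At stake is what the AUC can be said to show. The endpoint is worded as the ability to tell RBC-positive from RBC-negative regions, with no caveat about the reference. For the arterial wall, which is also labelled by experts, SAP 4.d does state that external validation is impossible. Secondary endpoints 4 (platelets) and 6 (fibrin) use the same method as the primary and inherit the problem.

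**Working it through.** **1. The plan's own figure.** Inputs (Protocol 15.5, SAP 6): AUC A = 0.85; 95% CI width at most 0.10; 5.44 measurements per acquisition; 3 acquisitions per intervention; 53% positive and 47% negative.

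Hanley–McNeil: SE² = [A(1−A) + (n₁−1)(q₁−A²) + (n₂−1)(q₂−A²)]/(n₁n₂), with q₁ = A/(2−A) = 0.7391 and q₂ = 2A²/(1+A) = 0.7811.

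- 14 interventions: n = 14 × 3 × 5.44 = 228.5, n₁ = 121.1, n₂ = 107.4. SE = 0.02535, width = 2 × 1.96 × SE = 0.0994.
- 13 interventions: width = 0.1031.

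So 14 is the minimum, and (11 + 14)/0.60 = 41.7, rounded up to 42. Both figures reproduce. The interval treats the labels as true and has no term for label error.

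**2. Where histology can help.** The pooled AUC is a proportion of positive–negative pairs. With K clots contributing equal numbers of measurements, and positive share p_k in clot k, the share of pairs from the same clot is (1/K) × mean[p_k(1−p_k)]/[p(1−p)], which is at most 1/K. For K = 14 that is 0.071. So at least 93% of pairs are between clots, where histology can inform the labels. The remainder, at most 7%, is the part that bears on local discrimination within a clot, and there full-clot histology offers no reference outside the signal.

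**3. How far label agreement and truth could part (illustration; the assumptions are not document figures).** True status is 53% positive. The signal separates true status with AUC s. Reader label and model score each equal the signal plus their own independent normal noise of SD σ, and histology is ignored. σ is set so that the AUC against labels is 0.85. The AUC against truth is then Φ(Φ⁻¹(s)/√(1+σ²)); the last column gives the simulated values.

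| s | σ | AUC vs labels | AUC vs truth |
|---|---|---|---|
| 0.50 | 0.60 | 0.85 | 0.50 |
| 0.60 | 0.61 | 0.85 | 0.59 |
| 0.70 | 0.64 | 0.85 | 0.67 |
| 0.80 | 0.70 | 0.85 | 0.75 |
| 0.90 | 0.85 | 0.85 | 0.84 |

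This is the extreme case. Use of histology in labelling would narrow the gap by an amount the documents do not let one compute.

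**4. The independent check.** Secondary endpoint 1 correlates model RBC output with core-lab histology at clot scale, at the 0.05 level.

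- Critical |r| = t/√(t² + n − 2). For n = 14, t = 2.179 and |r| = 0.53. The r for 80% power is about tanh(2.80/√11) = 0.69.
- With 60% of clots available (the figure in SAP 7), 14 × 0.60 = 8.4. For n = 8 the values are 0.71 and 0.85.

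Protocol 15.6 and SAP 8.c.vi report 30 clots analysed from the first 31 treated subjects, so a number near 14 is the likelier case.

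**The case against.** Much can be said for the plan. The reference standard is disclosed, as is the view that outsiders cannot apply it. Reading is double and independent with adjudication, and the model is fully fixed before validation. Histology from a blinded core lab enters the labels and also serves as a separate test in secondary endpoint 1. The bias sentence sits in a passage about the data split. The study is first-in-human and single-arm, 0.85 is a planning value and not a pass mark, the first objective is safety, and treating physicians are not shown the clot information.

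All of that stands, and it rules out several stronger readings that a reader might infer:

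- *The label is only the sponsor's reading of the signal.* SAP 4.b adds histology.
- *The AUC can say nothing about RBC content.* Histology can anchor the between-clot contrasts, which are most of the pairs.
- *The people who built the model also label, and will see its scores.* The documents do not say so. They are silent on access after lock, and Protocol 15.7 cites an internal procedure that is not public.
- *Many patients are labelled from the signal alone.* The population definitions permit patients without a retrieved clot, but 30 of 31 suggests that they will be few.

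What the objection does not remove is the shared signal, the lack of any external reference at local scale, and the missing statement on blinding after lock.

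**Conclusion.** The point holds, as a should-fix. The primary AUC measures agreement with expert labels that partly incorporate the index signal. Taken alone it does not establish local RBC accuracy. The split and lock deal with overfitting, so the bias sentence claims too much.

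The size of any upward bias cannot be bounded from the documents. The 0.50 to 0.84 range is a worst-case illustration resting on independent normal noise and no use of histology. It is not an estimate for this trial. The 7% bound assumes 14 clots with equal numbers of measurements. It would be wrong to infer that the AUC must approach 1 whatever the true composition: that requires readers to apply the model's own rule and to disregard histology, and the documents describe neither.

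**What to change.** 1. **Order and blinding.** In Protocol 15.7 and SAP 7, require validation labels to be completed, adjudicated and time-stamped before the locked model is run on validation data, with annotators blind to its scores. Use one wording for who is barred from validation data before lock.
2. **Wording.** Describe the primary result as agreement with expert labels, present secondary endpoint 1 beside it, and limit the bias sentence in Protocol 15.3 and SAP 8.c.i to overfitting. Apply the same description to secondary endpoints 4 and 6, each beside its own clot-scale comparison (endpoints 5 and 7).
3. **Reader agreement.** Report kappa from the two existing reads, the number of discordant readings, and the AUC on concordant as well as adjudicated labels. The concordant set probably drops the harder readings, so it is a sensitivity result.
4. **Alignment.** State the role of histology in Protocol 15.4.1 as in SAP 4.b. Reconcile Protocol 15.2 (tagged clot contact) with SAP 8.b (expert labelling) on which acquisitions enter validation. An AUC without the in-clot restriction should not be added unless an RBC label is defined for those readings.

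Cost: a narrower claim, a few extra table rows, and scoring that waits for core-lab histology. No new readers or patients are needed, and N stays at 42. The blinding step is the urgent one, because it cannot be restored once annotators have seen scores.

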### c) Secondary Endpoints

There are 7 secondary endpoints. The secondary endpoints are all performance endpoints and include:

1. The concordance between occlusion measurement done by CSGS, and the histopathology results of the clot retrieved during the EVT procedure, at the level of red blood cell content in the occlusion (clot scale).  
To determine the histopathological results of the clot, the mean will be taken of the percentage RBC composition of the 3 analyzed slices (value between 0 and 1) provided by the Core Lab.  
Significant correlation will be judged at the 0.05 significance level by the t-statistic of the relation between RBC content as output by the prediction model and the RBC content as quantified by the MSB-staining histological analysis
2. The ability of CSGS detecting the proximal end of the occlusion (sensor-scale), as compared to the physician's labelling (tag 'PRE-CLOT' for no occlusion contact) and tag 'CLOT' for occlusion contact). The concordance will be judged by the Area Under the Receiver Operator Characteristic curve on the validation set. The same methodology will be used as for the primary performance endpoint. Data from the interventions in the development and validation sets will be the same as for the primary endpoint.
3. Procedural success defined as the ability to navigate CSGS to the occlusion and measure electrophysiological properties of the occlusion. Procedural success is achieved from the moment that at least 1 effective measurement is captured by the CSGS in or beyond the clot.
4. The ability to perform binary classification of individual electrophysiological parameter measurements (local scale) by distinguishing local regions with substantial platelet content (platelet-positive) from regions with negligible platelet content (platelet-negative) in the occlusion. The ability to perform binary classification will be evaluated by the performance metric area under the ROC curve computed from the platelet-content score predicted on the validation set. The same methodology will be used as for the primary performance endpoint.
5. The concordance between aggregated occlusion measurements (clot scale) done by CSGS, and the histopathology results of the clot retrieved during the EVT procedure, regarding platelet content in the occlusion.  
To determine the histopathological results of the clot, the platelet composition (value between 0 and 1) will be averaged over the 3 analyzed slides provided by the Core Laboratory.  
Significant correlation will be judged at the 0.05 significance level by the t-statistic of the relation between platelet content as output by the prediction model and the platelet as quantified by the CD42b immunochemistry staining histological analysis.
6. The ability to perform binary classification of individual electrophysiological parameter measurements (local scale) by distinguishing local regions with substantial fibrin content (fibrin-positive) from regions with negligible fibrin content (fibrin-negative) in the occlusion. The ability to perform binary classification will be evaluated by the performance metric area under the ROC curve computed from the fibrin-content score predicted on the validation set. The same methodology will be used as for the primary performance endpoint.
7. The concordance between aggregated occlusion measurements (clot scale) done by CSGS, and the histopathology results of the clot retrieved during the EVT procedure, regarding fibrin content in the occlusion.  
To determine the histopathological results of the clot, the fibrin composition (value between 0 and 1) will be averaged over the 3 analyzed slides provided by the Core Laboratory.

Significant correlation will be judged at the 0.05 significance level by the t-statistic of the relation between fibrin content as output by the prediction model and the fibrin content as quantified by the MSB-staining histological analysis.

